8.3.5. Laboratory Assessments

8.3.5.1. Safety Assessments

Required laboratory tests are listed in Table 10. Safety laboratory tests include hematology, chemistry, CRP, and lipid panel (see Table 3). Participants may have a light snack before this visit, but should allow for an overnight fast (at least 8 hours) before sample collection for the lipid panel.

If there is any abnormality in hematology assessment (particular for platelet counts) at Week 2, an unscheduled visit at Week 3 (see Section 8.6) to repeat hematology assessments will be required.

Clinical laboratory tests will be performed at a central laboratory (see the Laboratory Manual for sample handling and shipping instructions).

8.3.5.2. Screening Assessments

Screening laboratory tests include urinalysis, serology, TB screening, pregnancy test, and an FSH test for confirmation of nonchildbearing status in women who are postmenopausal, defined as amenorrhea at least 12 months before screening. See the Laboratory Manual for screening assessment instructions.

8.3.5.3. Pregnancy Test

A serum pregnancy test will be required for all women of childbearing potential during screening. Urine pregnancy tests will be conducted as outlined in Table 3, as medically indicated, or per country-specific requirement. Urine pregnancy tests will be performed locally. If a urine pregnancy test is positive, the results should be confirmed with a serum pregnancy test, which may be performed locally.

b Postdose ECGs will be performed when participants arrive at the study sites

If abnormality ECG results are observed, an additional 2 ECGs will be measured within the next 5 minutes. Postdose

[figure not shown]
ECG will be measured

c Day 1 predose 12-lead ECGs will be performed in triplicate, and values will be averaged to calculate the baseline values.

Note: Single → Triple: Single ECG will be performed first. If abnormal ECG results are observed, an additional 2 ECGs will be measured within the next 5 minutes.

If the serum pregnancy test is negative after a urine test was positive, the investigator will assess the potential benefit/risk to the participant and determine whether it is in the participant's best interest to resume study drug and continue participation in the study.

If a pregnancy is confirmed by a serum pregnancy test, see Section 9.6 for reporting requirements.

8.6. Unscheduled Visits

Unscheduled visits may occur at any time at the investigator's discretion, and appropriate clinical and laboratory tests may be performed, as clinically indicated.

If there is any abnormality in hematology assessment (particular for platelet counts) at Week 2, an unscheduled visit at Week 3 to repeat hematology assessments will be required. Refer to Section 6.5 for the instruction of dose interruption and restart. The investigator must inform and consult sponsor with any hematological abnormality.

8.7. End of Treatment and/or Early Termination

If a participant permanently discontinues study drug or has completed the protocol-specified duration of treatment, an EOT visit should be conducted. If the EOT visit coincides with a regular study visit, the EOT evaluations will supersede those of that scheduled visit, and the data should be entered in the EOT visit in the eCRF. The participant should be encouraged to return for the follow-up visit.

8.8. Follow-Up

8.8.1. Safety Follow-Up

The safety follow-up period is the interval between the EOT visit and the scheduled safety follow-up visit, which should occur 28 to 35 days after the EOT visit (or after the last dose of study drug if the EOT visit was not performed). Adverse events and SAEs must be reported up until the end of follow-up period, the date of the follow-up visit, or until toxicities resolve, return to baseline, or are deemed irreversible, whichever is longer. Reasonable efforts should be made to have the participant return for the follow-up visit and report any AEs that may occur during this period.

For purposes of analysis, participants who complete through Week 8 will be considered to have completed the study.

9. ADVERSE EVENTS: DEFINITIONS AND PROCEDURES FOR RECORDING, EVALUATING, FOLLOW-UP, AND REPORTING

9.1. Definition of Adverse Event

Adverse Event Definition

- An AE is any untoward medical occurrence associated with the use of a drug in humans, whether or not considered drug-related.
- An AE can therefore be any unfavorable and unintended sign (including an abnormal laboratory finding), symptom, or disease (new or exacerbated) temporally associated with the use of study treatment.

Events Meeting the Adverse Event Definition

- Any safety assessments (eg, ECG, vital signs measurements), including those that worsen from baseline, considered clinically significant in the medical and scientific judgment of the investigator (ie, not related to progression of underlying disease).
- Abnormal laboratory test results constitute an AE if they are considered clinically meaningful, induce clinical signs or symptoms, require concomitant therapy, or require changes in study drug. Whenever possible, a diagnosis (eg, anemia, thrombocytopenia) should be recorded in the eCRF rather than the abnormal lab result (eg, low hemoglobin, platelet count decreased).
- Exacerbation of a chronic or intermittent pre-existing condition including either an increase in frequency and/or intensity of the condition.
- New conditions detected or diagnosed after study treatment administration even though it may have been present before the start of the study.
- Signs, symptoms, or the clinical sequelae of a suspected drug-drug interaction.
- Signs, symptoms, or the clinical sequelae of a suspected overdose of either study treatment or a concomitant medication. Overdose per se will not be reported as an AE/SAE unless it is an intentional overdose taken with possible suicidal/self-harming intent. Such overdoses should be reported regardless of sequelae.
- "Lack of efficacy" or "failure of expected pharmacological action" per se will not be reported as an AE or SAE. Such instances will be captured in the efficacy assessments. However, the signs, symptoms, and/or clinical sequelae resulting from lack of efficacy will be reported as AE or SAE if they fulfil the definition of an AE or SAE.

Events NOT Meeting the Adverse Event Definition

- Any clinically significant abnormal laboratory findings or other abnormal safety assessments that are associated with the underlying disease, unless judged by the investigator to be more severe than expected for the participant's condition.
- The disease/disorder being studied or expected progression, signs, or symptoms of the disease/disorder being studied, unless more severe than expected for the participant's condition or considered to be treatment-related by the investigator.
- Medical or surgical procedure (eg, endoscopy, appendectomy): the condition that leads to the procedure is the AE if it occurred after signing the ICF. If present before entering the study, the condition should be captured as medical history.

- Situations in which an untoward medical occurrence did not occur (social and/or convenience admission to a hospital).
- Anticipated day-to-day fluctuations of pre-existing disease(s) or condition(s) present or detected at the start of the study that do not worsen.

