6.5. Dose Modifications

In some circumstances, it may be necessary to temporarily interrupt treatment with INCB054707 as a result of AEs or laboratory abnormalities that have an unclear relationship to the study drug (see Table 7). Except in cases of emergency, it is recommended that any laboratory findings be confirmed and that the investigator consult with the sponsor medical monitor (or other representative of the sponsor) before temporarily interrupting study drug.

Table 7: Guidelines for Interrupting, Restarting, and Discontinuing Study Drug

ADVERSE EVENT	ACTION TAKEN	
Chemistry		
AST and/or ALT > 3.0 × ULN	 Step 1: Interrupt study drug administration up to 2 weeks (14 days) until the toxicity has resolved to ≤ 3.0 × ULN. Step 2: Restart study drug, and monitor as clinically indicated. 	
AST and/or ALT > 5.0 × ULN	Discontinue study drug administration, and monitor as described in Section 9.3.	
Hematology		
Platelet counts 50 to ≤ 100 × 109/L or ≥ 50% decrease from baseline	Step 1: Interrupt study drug administration up to 2 weeks (14 days) until the toxicity has resolved to $> 100 \times 10^9/L$.	
	Step 2: Restart study drug, and monitor as described in Section 9.3.	
$ANC \le 1.0 \times 109/L$	Step 1: Interrupt study drug administration up to 2 weeks (14 days) until the toxicity has resolved to $> 1 \times 10^9/L$ or the baseline value.	
	Step 2: Restart study drug, and monitor as clinically indicated.	
Hemoglobin 8 to ≤ 10 g/dL	Step 1: Interrupt study drug administration up to 2 weeks (14 days) until the toxicity has resolved to > 10 g/dL.	
	Step 2: Restart study drug, and monitor as clinically indicated.	
 Platelet count < 50 × 10⁹/L ANC < 0.5 × 10⁹/L 	Discontinue study drug administration, and monitor as described in Section 9.3.	
• ANC ≤ 1.0 × 10 ⁹ /L with an oral temperature of at least 38.5°C OR with ≥ Grade 3 infection		
• Hemoglobin < 8 g/dL		

Table 7: Guidelines for Interrupting, Restarting, and Discontinuing Study Drug (Continued)

ADVERSE EVENT	ACTION TAKEN	
Other toxicities		
Any Grade 1 or Grade 2 toxicity	Continue study drug and treat the toxicity; monitor as clinically indicated.	
Any Grade 3 toxicity except those that are clearly and incontrovertibly due to underlying disease or extraneous causes	 Step 1: Interrupt study drug up to 2 weeks (14 days), until toxicity resolves to ≤ Grade 1. Step 2: Restart study drug and monitor as clinically indicated. 	

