8.2.2. Adverse Event Summaries

An overall summary of AEs will include:

- Number (%) of participants reporting any TEAEs
- Number (%) of participants reporting any SAEs
- Number (%) of participants reporting any Grade 3 or 4 TEAEs
- Number (%) of participants reporting any treatment-related TEAEs
- Number (%) of participants who temporarily interrupted study treatment because of TEAEs

- Number (%) of participants who permanently discontinued study treatment because of TEAEs
- Number (%) of participants who had a TEAE leading to death

The following summaries will be produced by MedDRA term (if 2 or fewer participants appear in a table, a listing may be appropriate):

- Summary of TEAEs by SOC and PT
- Summary of TEAEs by PT in decreasing order of frequency
- Summary of TEAEs by SOC, PT, and maximum severity
- Summary of treatment-related AEs by SOC and PT
- Summary of treatment-related AEs by PT in decreasing order of frequency
- Summary of treatment-related AEs by SOC, PT, and maximum severity
- Summary of Grade 3 or 4 AEs by SOC and PT
- Summary of Grade 3 or 4 treatment-related AEs by SOC and PT
- Summary of TEAEs leading to death by SOC and PT
- Summary of treatment-emergent SAEs by SOC and PT
- Summary of treatment-emergent SAEs by PT in descending order of frequency
- Summary of treatment-related SAEs by SOC and PT
- Summary of TEAEs leading to dose interruption by SOC and PT
- Summary of TEAEs leading to discontinuation of treatment by SOC and PT
- Summary of nonserious TEAEs by SOC and PT

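### Section 9.1 has two overlapping rules on laboratory abnormalities with no stated precedence, so an interruption attributed to HS could be missing from the AE and interruption tables

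*Protocol*

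**What the plan says.** Protocol Section 9.1 holds both rules.

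- In the list of events that meet the AE definition, an abnormal laboratory result qualifies if it is clinically meaningful or if it should "induce clinical signs or symptoms, require concomitant therapy, or require changes in study drug". That bullet makes no exception for cause.
- The list of events that do not meet the definition includes "Any clinically significant abnormal laboratory findings or other abnormal safety assessments that are associated with the underlying disease", with the proviso "unless judged by the investigator to be more severe than expected" for the participant's condition.

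Protocol Section 6.5 says that treatment may need to be interrupted "as a result of AEs or laboratory abnormalities that have an unclear relationship to the study drug". It thus names AEs and laboratory abnormalities as separate triggers. In Table 7 the chemistry and hematology rows are defined by the value; the hemoglobin interruption row, for instance, reads "Hemoglobin 8 to ≤ 10 g/dL". The only exception for underlying disease is in the other-toxicities part of the table: "Any Grade 3 toxicity except those that are clearly and incontrovertibly due to underlying disease or extraneous causes".

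SAP Section 8.2.2 plans "Number (%) of participants who temporarily interrupted study treatment because of TEAEs" in the overall summary, and a table by system organ class and preferred term (Table 3.2.14) that is also restricted to TEAEs. SAP Section 6.4 summarises duration of treatment, average daily dose and total dose. No planned table counts interruptions for any cause.

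**The concern.** Whether the suspected cause is HS or the drug is a causality question, and the protocol has a causality field for it (Section 9.3). The exclusion bullet lets that attribution decide earlier whether an AE record exists at all. A laboratory result can make the investigator stop dosing and, on a literal reading of the second rule, still generate no AE. Because the SAP reaches interruptions only through TEAEs, such an interruption would be counted in neither the AE incidence tables nor the interruption tables.

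The study is open-label and single-arm, and its primary endpoint includes the frequency, duration and severity of AEs. The investigator making the attribution knows that the participant is on drug, and no control group shows how often the same abnormality arises from HS alone. Two sites could classify the same result differently and both be following the protocol.

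**Working it through.** There is no power, alpha or derived sample size to reproduce: both documents say that the sample size follows precedent. The check is a reading of the rules against each other, followed by simple arithmetic.

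**1. Do the two rules collide?** Take a result inside a Table 7 interruption range that the investigator attributes to HS and considers no worse than expected.

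- First rule: study drug had to be changed, so it is an AE.
- Second rule: it is associated with the underlying disease and the proviso is not met, so it is not an AE.
- Precedence: none is stated in Section 9.1.

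The neighbouring bullet on disease signs and symptoms restores AE status if the investigator considers the event treatment-related. The laboratory bullet has no such clause.

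**2. Which Table 7 rows can produce such a result?** Compare the least extreme eligible value (Section 5.2) with the start of the interruption range (Table 7).

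| Parameter | Eligibility limit | Interruption range starts | Change needed |
|---|---|---|---|
| Platelets (10⁹/L) | 150 | 100 | (150 − 100)/150 = 33% fall |
| ANC (10⁹/L) | 1.5 | 1.0 | (1.5 − 1.0)/1.5 = 33% fall |
| ALT/AST (× ULN) | below 1.5 | above 3.0 | 3.0/1.5 = 2, so more than a doubling |
| Hemoglobin (g/dL) | 10 | 10 | 10 − 10 = 0 |

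The platelet row can also be triggered by a fall of at least 50% from baseline, which is itself a marked worsening. In the first three rows the participant must worsen clearly on treatment, which makes it hard to argue that the result is no worse than expected. Hemoglobin differs. Exclusion is below 10 g/dL at screening and the interruption range includes 10 g/dL, so an eligible and unchanged value of exactly 10 already lies in the range.

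**3. Where would the case appear if no AE were recorded?**

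- Absent: TEAE incidence tables, treatment-related AE tables, the TEAE-interruption count and Table 3.2.14.
- Present: worst-grade and shift tables and the abnormal-value listings for the laboratory result (SAP 8.3.2, Appendix A); the Study Drug Administration listing; total dose and average daily dose (SAP 6.4); compliance (SAP 6.5).
- For a permanent discontinuation, also the disposition summary by primary reason (SAP 6.2, Table 1.1.2).

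**4. How visible is it in the exposure summaries?** As an illustration, take the longest interruption in Table 7, 14 days, within 8 weeks (56 days) at one 15 mg tablet daily, with otherwise full dosing. Total dose is 42 × 15 = 630 mg against 56 × 15 = 840 mg. Average daily dose is 630/56 = 11.25 mg. Compliance is 42/56 = 75%, assuming that the intended tablet count is not reduced for the interruption. The interruption leaves a trace, but these summaries cannot tell it from 14 missed doses.

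**5. Size in the interruption table.** With n = 10, one participant is 1/10 = 10 percentage points. The exact 95% limits are Beta⁻¹(0.025; x, n − x + 1) and Beta⁻¹(0.975; x + 1, n − x).

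- 2/10 = 20% (2.5% to 55.6%)
- 1/10 = 10% (0.25% to 44.5%)
- 0/10 = 0% (0% to 30.8%; the upper limit is 1 − 0.025^(1/10))

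One unrecorded case turns 2/10 into 1/10, or 1/10 into 0/10. The any-TEAE proportion falls only if that participant has no other TEAE.

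**The case against.** The strongest reply is that the protocol already leans towards recording these events. Table 7 heads its trigger column as adverse events and calls them toxicities, and several laboratory rows send the reader to Section 9.3, the AE recording section. Section 9.1 counts an increase in the intensity of a pre-existing condition as an AE and gives anemia as an example of a diagnosis to record. Section 8.3.1 requires AEs to be recorded whatever the assumed relationship to study drug. Section 9.3 lists underlying disease among the alternative causes to weigh. Table 7 is presented as guidelines, Section 6.5 recommends confirmation and consultation before interrupting, and Section 8.6 requires the sponsor to be consulted on any hematological abnormality. A silent reclassification at a site is therefore unlikely. The documents also name no laboratory abnormality as a feature of HS.

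Much of this stands, and it narrows the point. It does not settle it. The Table 7 heading is offset by Section 6.5, which treats laboratory abnormalities as a trigger separate from AEs. The recording rule in Section 8.3.1 applies to events that are already AEs. Consultation with the sponsor does not say which bullet of Section 9.1 prevails.

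A reader might infer three stronger things that the documents do not support:

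- That Table 7 interruptions in general can drop out. The proviso on severity returns many findings to AE status, and platelet, ANC and ALT/AST interruptions need on-treatment worsening.
- That discontinuations are reached only through TEAEs. SAP Section 6.2 also summarises them by primary reason.
- That the event would survive only in the laboratory tables or be lost from the primary endpoint. Laboratory results are themselves named in the primary endpoint, and the dosing listing, exposure and compliance outputs also carry a trace.

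**Conclusion.** The contradiction in Section 9.1 is real, and its reach is narrow. It affects a laboratory-driven interruption that the investigator both attributes to HS and judges no worse than expected. Such a case could be missing from the AE tables and from the TEAE-based interruption count and table. Hemoglobin is the most plausible route, because its eligibility limit and its Table 7 interruption range meet at 10 g/dL. Those two passages must be reconciled; no threshold is proposed here.

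Each such case shifts the TEAE-interruption proportion by 10 percentage points, assuming 10 treated participants; with fewer, the shift is larger. How often it would happen depends on how often investigators attribute such abnormalities to HS, which the documents do not give. No hypothesis test or decision threshold rests on the count. What is at stake is whether primary safety events are counted in the same way at every site.

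**What to change.** In Protocol Section 9.1, state the precedence: a laboratory abnormality that leads to interruption or discontinuation of study drug is recorded as an AE whatever its suspected cause, and the suspected cause is entered under causality. Reconcile the hemoglobin limit in Section 5.2 with the hemoglobin row of Table 7.

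In the SAP, add the number and percentage of participants with any dose interruption, taken from the dosing record, and reconcile it with the action taken on the AE form. Discontinuations by reason are already in the disposition summary and need only the same cross-check.

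The cost is one clause on AE recording, the reconciliation of the two hemoglobin passages, one added table row and a reconciliation step. The downside is a few more laboratory AEs, some unrelated to study drug. The recording clause and the SAP count change no dose, threshold or interruption rule.

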9.2. Definition of Serious Adverse Event

If an event is not an AE per the definition above, then it cannot be an SAE even if serious conditions are met (eg, hospitalization for signs/symptoms of the disease under study, death due to progression of disease).

A Serious Adverse Event is defined as any untoward medical occurrence that, at any dose:

a. Results in death

b.Is life-threatening

The term "life-threatening" in the definition of "serious" refers to an adverse drug experience that places the participant, in the opinion of the initial reporter, at immediate risk of death from the adverse experience as it occurred. This does not include an adverse drug experience that, had it occurred in a more severe form, might have caused death.

c. Requires inpatient hospitalization or prolongation of existing hospitalization

In general, hospitalization signifies that the participant has been detained (usually involving at least an overnight stay) at the hospital or emergency ward for observation and/or treatment that would not have been appropriate in the physician's office or outpatient setting. Complications that occur during hospitalization are AEs. If a complication prolongs hospitalization or fulfills any other serious criteria, the event is serious. When in doubt as to whether "hospitalization" occurred or was necessary, the AE should be considered serious.

Hospitalization for elective treatment of a pre-existing condition that did not worsen from baseline is not considered an AE.

d. Results in persistent or significant disability/incapacity

- The term disability means a substantial disruption of a person's ability to conduct normal life functions.
- This definition is not intended to include experiences of relatively minor medical significance, such as uncomplicated headache, nausea, vomiting, diarrhea, influenza, and accidental trauma (eg, sprained ankle), that may interfere with or prevent everyday life functions but do not constitute a substantial disruption.

e. Is a congenital anomaly/birth defect

f. Other situations (Important Medical Event):

An event that may not result in death, be immediately life-threatening, or require hospitalization, but may be considered serious when, based on appropriate medical judgment, the event may jeopardize the participant and may require medical or surgical intervention to prevent one of the outcomes listed in the above definition. Examples of such events include invasive or malignant cancers, intensive treatment in an emergency department or at home for allergic bronchospasm, blood dyscrasias, or convulsions that do not result in hospitalization, or development of drug dependency or drug abuse.

9.3. Recording an Adverse Event and/or Serious Adverse Event

Adverse Event and Serious Adverse Event Recording

- An AE/SAE that begins or worsens after informed consent is signed should be recorded on the Adverse Event Form in the eCRF. Conditions that were present at the time informed consent was given should be recorded on the Medical History Form in the eCRF.
- When an AE/SAE occurs, it is the responsibility of the investigator to review all documentation (eg, hospital progress notes, laboratory reports, and diagnostics reports) related to the event.
- The investigator (or delegate) will then record all relevant AE/SAE information in the eCRF.
- It is **not** acceptable for the investigator to send photocopies of the participant's medical records to sponsor or designee in lieu of completion of the AE eCRF page.
- There may be instances when copies of medical records for certain cases are requested. In this case, all participant identifiers, with the exception of the participant number, will be redacted on the copies of the medical records before submission.
- The investigator will attempt to establish a diagnosis of the event based on signs, symptoms, and/or other clinical information. Whenever possible, the diagnosis (not the individual signs/symptoms) will be documented as the AE/SAE. When a clear diagnosis cannot be identified, each sign or symptom should be reported as a separate AE/SAE.

To the extent possible, each AE/SAE should be evaluated to determine:

- The severity grade (CTCAE Grade 1 to 5). See below for further instructions on the assessment of intensity.
- Whether there is at least a reasonable possibility that the AE is related to the study drug: suspected (yes) or not suspected (no). See below for further instructions on the assessment of causality.
- The start and end dates, unless unresolved at final follow-up.
- The action taken with regard to study drug as a result of the AE/SAE(s).
- The event outcome (eg, not recovered/not resolved, recovered/resolved, recovering/resolving, recovered/resolved with sequelae, fatal, unknown).
- The seriousness, as per the SAE definition provided in Section 9.2.
- The action taken with regard to the event. Note: If an AE is treated with a concomitant medication or nondrug therapy, this action should be recorded on the Adverse Event Form, and the treatment should be specified on the appropriate eCRF (eg, Prior/Concomitant Medications, Procedures and Non-Drug Therapy).

Assessment of Intensity

The severity of AEs will be assessed using CTCAE v4.03 Grades 1 through 5. If an event is not classified by CTCAE, the severity of the AE will be graded according to the scale below to estimate the grade of severity.

The investigator will make an assessment of intensity for each AE and SAE reported during the study and assign it to 1 of the following categories:

- **Grade 1:** Mild; asymptomatic or mild symptoms; clinical or diagnostic observations only; intervention not indicated.
- **Grade 2:** Moderate; minimal, local, or noninvasive intervention indicated; limiting age appropriate activities of daily living.
- **Grade 3:** Severe or medical significant but not immediately life-threatening; hospitalization or prolongation of hospitalization indicated; disabling; limiting self-care activities of daily living.

- Grade 4: Life-threatening consequences; urgent intervention indicated.
- Grade 5: Fatal.

Assessment of Causality

- The investigator is obligated to assess the relationship between study treatment and each occurrence of each AE/SAE.
- A "reasonable possibility" of a relationship conveys that there are facts, evidence, and/or arguments to suggest a causal relationship, rather than that a relationship cannot be ruled out.
- The investigator will use clinical judgment to determine the relationship.
- The investigator will also consult the RSI in the IB and/or Product Information, for marketed products, in his/her assessment.
- Alternative causes, such as underlying disease(s), concomitant therapy, and other risk factors, as well as the temporal relationship of the event to study treatment administration will be considered and investigated.
- For each AE/SAE, the investigator **must** document in the medical notes that he/she has reviewed the AE/SAE and has provided an assessment of causality.
- With regard to assessing causality of SAEs:
 - There may be situations in which an SAE has occurred and the investigator has minimal information to include in the initial report to the sponsor or designee. However, it is very important that the investigator always make an assessment of causality for every event before the initial transmission of the SAE data to sponsor or designee.
 - The investigator may change his/her opinion of causality in light of follow-up information and send a SAE follow-up report with the updated causality assessment.

Follow-Up of Adverse Events and Serious Adverse Events

- The investigator is obligated to perform or arrange for the conduct of supplemental measurements and/or evaluations as medically indicated or as requested by the sponsor or designee to elucidate the nature and/or causality of the AE/SAE as fully as possible. This may include additional laboratory tests or investigations, histopathological examinations, or consultation with other healthcare professionals.
- If a participant dies during participation in the study or during a recognized follow-up period, the investigator will provide the sponsor or designee with a copy of any postmortem findings, including histopathology.
- New or updated information will be recorded in the originally completed eCRF.
- Any updated SAE data to the sponsor or designee within 24 hours of receipt of the information.
- Once an AE is detected, it should be followed until it has resolved or until it is judged to be permanent; assessment should be made at each visit (or more frequently if necessary) of any changes in severity, the suspected relationship to the study drug, the interventions required to treat the event, and the outcome.
- When the severity of an AE changes over time for a reporting period (eg, between visits), each change in severity will be reported as a separate AE until the event resolves.

